
III. STUDY OBJECTIVES

To test Perception Threshold Tracking (PTT) and multi-level MRI as methods for early detection and grading of severity of neuropathy in patients with diabetes mellitus.

To use multi-level MRI for characterization of peripheral and central nervous system changes related to neuropathy in patients with diabetes mellitus.

To compare Perception Threshold Tracking (PTT) and MRI to methods of traditional clinical practice and established methods of clinical research like Corneal Confocal Microscopy (CCM) and Quantitative Sensory Testing (QST) as well as axon flair-mediated neurogenic vasodilation (AF).

To test reliability of different measurements of neuropathy.

A better understanding of the underlying neuropathy of diabetes and new methods for early, reliable detection of DPN could result in intensified treatment and prophylactic measures prolonging of the complicationfree period of diabetes mellitus. Ultimately, this could potentially result in fewer complications related to the diabetic foot, and maybe even prolonged overall-survival and reduced healthcare cost.

IV. METHODS

A. Study Design

This study is a prospective, observational, cross-sector study starting March 1, 2019 running until December 1, 2021. The study will be conducted on patients from Aalborg University Hospital. Participants will be informed about the trial both written and vocally and no changed in antidiabetic medication will be performed. The instruments will include Corneal Confocal Microscopy (CCM), Quantitative Sensory Testing (QST), axon flair-mediated neurogenic vasodilation (AF), handheld heart rate measurement device (Vagus[™]), cuff, and MRI, which are all established methods of clinical research. Furthermore, participants will be tested using monofilament and Biothesiometry, which equals actual clinical practice, and with Perception Threshold Tracking (PTT), which is a new take on an older, well-known technology. Further tests will include a handheld pinprick device, measurements of peripheral arterial disease (PAD) and conventional NCS. The main endpoint of the study will be sensitivity/specificity of all examinations, as well as a comparison of the newer methods against more well-established modalities.

B. Study Population

The study population include four well-defined groups of subjects:

- 1. Patients with Type 1 diabetes and painful diabetic peripheral neuropathy (DPN).

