- 2. Patients with Type 1 diabetes and non-painful diabetic peripheral neuropathy (DPN)
- 3. Patients with Type 1 diabetes and without diabetic peripheral neuropathy (DPN).
- 4. Healthy control subjects matched for age, BMI, and gender.

Diabetes duration, HbA1c, insulin use, ethnicity, and co-morbidities will be matched between group 1, 2 and 3 to best ability.

Inclusion criteria:

- 1. Men and women minimum 18 years of age and maximum 70 years of age
- 2. Signed informed consent form
- 3. Diagnosed with diabetes type I (for group 1-3)
- 4. Diagnosed with DPN defined as a threshold above 25-volt biothesiometry or absent feeling on the big toe using 10g-monofilament. (for group 1-2)
- 5. Answered questionnaire: PainDETECT
- 6. Nothing abnormal on initial tests (group 4)
- 7. Accepted initial screening blood samples
- 8. MRI-compatible participant

Exclusion criteria:

1. Current or previous alcohol- or drug abuse

- 2. Abnormal screening blood samples
- 3. Not being able to understand Danish written and/or verbally
- 4. Not being able to corporate to examination (e.g. not being able to speak, suffering from senile dementia etc.)
- 5. Previous chemotherapy or intake of experimental medicine
- 6. Active HSV- or VZV-infection or known HIV
- 7. Known severe skin disease
- 8. Known neural damage or disease in the neural system (e.g. MS, Guillain-Barre etc.)
- 9. Critical limb ischemia defined as in current clinical consensus[63]
- 10. Allergy or intolerance to histamine or inability to make do without for one day
- 11. Pregnancy
- 12. Active cancer-disease

C. Assessment of Resources

The study will be conducted in collaboration with Steno Diabetes Center Northern Denmark (SDCN) and Department of Radiology, Aalborg University Hospital. SDCN has access to patients with diabetes and can provide the necessary premises.

The study will be conducted in collaboration with Center for Neuroplasticity and Pain (CNAP), Aalborg University and SDCN, who have the technical and financial resources needed to establish the setup and conduct the examinations. Furthermore, an experienced research Bio. Med. Lab. Technologist is signed for the project thereby, alongside the Ph.D.-students, ensuring trained personnel. The study is set for a long inclusion, but additional time is available if required, as the Ph.D.-students are employed until 31st of October 2022.

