The project is initiated by [name], Aalborg University and SDCN, and is supported economically by Steno Diabetes Center North Denmark and Aalborg University. The support is however limited to staff salary and purchase of smaller equipment.

D. Study Procedures

Diabetic patients will be recruited during their scheduled visit to the outpatient clinic of SDCN, Aalborg University Hospital. Healthy controls will be recruited based on the included diabetic population using relatives of diabetic patients, medical students, and people known by participating staff.

After the informed consent is obtained the screening of the participant will be executed. Afterwards the participant have to attend three different sessions as shown in appended flowchart. Each session includes different tests and the sessions will be ordered randomly, since they have no influence on each other. Moreover, a conventional nerve conduction test will be performed, however this test will be performed as per usual by the department of neurophysiology, as this is a standard examination for patients with neuropathy.

PainDETECT

PainDETECT is an English questionnaire validated for detecting neuropathic pain[64]. It has later been translated and validated in Danish[65], and will be given each participant alongside instructions after form of consent has been signed. The patients will answer the questionnaire individually and will need to complete this before any other examinations can be conducted, as this will help placing the patients in the correct group.

Estimated time: 5-15 min.

Clinical examination

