Quantitative Sensory Testing (QST) is a way of assessing large and small sensory nerve fiber function using several different stimuli. The method has been verified using different protocols, and will be conducted in

accordance to the original protocol by German Research Network on Neuropathic Pain (DFNS)[66]. All measurements are made on the dorsum of the foot. The test will be conducted by either PhD-students or research bio. med. lab. Technologist. The protocol consists of seven tests measuring 13 parameters including:

1) Thermal detection, thermal pain thresholds and paradoxical heat sensations:

The tests for thermal sensation will be performed using a thermal sensory testing device. Cold detection threshold (CDT) and warm detection threshold (WDT) are measured initially and the number of paradoxical heat sensations (PHS) are counted. Cold pain threshold (CPT) and heat pain threshold (HPT) are then calculated as a mean threshold temperature of three consecutive measurements. All thresholds are to be obtained with ramped stimuli increasing by 1 degree Celsius per second, terminated as the patient presses a button. Cut-off temperatures are set at zero and 50 degree Celsius and the baseline temperature is set at 32 degree Celsius, as this represents the mean value of skin temperature.

2) Mechanical detection threshold for modified von Frey filaments

Mechanical detection threshold (MDT) is to be measured using a standardized set of modified von Frey hairs that exert forces between 0.25 and 512 mN. The final threshold will be the geometric mean of five series of ascending and descending stimulus intensities.

3) Mechanical pain threshold for pinprick stimuli

Mechanical pain threshold (MPT) is to be measured using thin, blunt, weighted pinprick stimulators that exert forces between 8 and 512 mN. The set will consist of seven different stimulators and the MPT will be the mean of five series.

4) Mechanical pain sensitivity and dynamic mechanical allodynia

Mechanical pain sensitivity (MPS) is to be tested using the same weighted pinprick stimuli as for MPT (see above). To obtain a stimulus–response-function, the seven pinprick stimuli is applied in a balanced order, five times each, and the subject is asked to give a pain rating for each stimulus on a 0–100 numerical rating scale with 0 being no pain and 100 being worst pain imaginal.

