Axon flair-mediated neurogenic vasodilation (AF) uses Laser Doppler flowmetry (LDF) [66] or laser Doppler imaging (LDI) [67] to analyze vasomotor small fiber function by quantifying the integrity of the vasomotor-mediated axon reflex. While LDF assesses the flare response following acetylcholine iontophoresis with temporal resolution at a single defined skin point, LDI records flare responses with spatial and temporal resolution, generating a two-dimensional map of superficial blood flow [61]. In this study, the participants' surface skin temperature of the dorsum of the foot will be standardized to 32 degree Celsius using a warm blanket or warming pad. Either histamine or Acetylcholine will then be applied to a small area and vasodilation will be measured in accordance to earlier studies[67].

Estimated time: 15-20 min

Perception Threshold Tracking

Perception Threshold Tracking (PTT) is a potential new method for early detection of neuropathy. It is a further development of conventional threshold tracking[68] that excels in describing membrane potential of not only large, but also small nerve fibers[62]. The trial is conducted using two types of surface electrodes placed on the dorsum of the foot: patch and pin electrodes for stimulation of large and small nerve fibers respectively. The perception threshold is then estimated by slowly increasing the intensity of stimuli until the patient presses a button indicating that the stimuli is perceived. As this happens, the intensity is initially heighted by 20 % and then lowered until the patient relieves the button indicating that the stimulus is no longer felt. The intensity is then lowered by 20% and then increased until perception is indicated by pressing the button. This is repeated three to five times to increase precision. The perception threshold is taken as the average of the six to ten times the patient pressed the button. This procedure will be repeated a number of times using different electrodes. The patient will feel no significant pain, as the stimuli given is just around the individual perception threshold, which is a huge benefit of this method compared to other available neural tests.

Estimated time: 35-45 min

Multi-Level Magnetic Resonance Imaging

The multi-level MRI will be used to assess brain structure, function and metabolism and the peripheral nerve structure and function. The MRI session will consist of 1) an anatomical 3D scanning of the brain, 2) functional

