The blood samples will be taken and handled as usual by the biochemical department and will be destroyed after usage. No biobank will be made. All samples will start being analyzed immediately (within 2h), however, some samples (like vitamin D) will take some time to analyze. All results will be available within 10-12 days but samples will always be destroyed as soon as the analysis has been initialized.

V. DATA COLLECTION

Patient data will be collected using the electronic patient journal (EPJ) after consent of the participant. Only patients with an active continuity of care at SDCN will be included (as well as healthy controls). The principle investigator is employed at SDCN as a medical doctor alongside one of the Ph.D.-students.

Data collected will include demographic data such as name, age, sex, weight, and height, and clinical information related to diabetes, such as type, duration, medication, complicating peripheral arterial disease, and status of complications. This to ensure correct grouping of the patients and to make sure that they meet the inclusion criteria.

VI. DATA ANALYSIS

A. Sample Size Considerations

The following sample size estimation is made on the ability to separate a group of diabetic patients without neuropathy from a group of diabetes patients with 'moderate' neuropathy. The calculations are based on published measurement of the sensory nerve action potential amplitude in nerve fiber conduction assessments[45]. Setting the significance level to 0.05 and the power to 0.8 results in a sample size estimation of 16 persons in each group. $n = \frac{15.7*\sigma^2}{d^2} = \frac{15.7*(4.7^2+7.5^2)}{(14.4-5.7)^2} = 16$. The study involves several experiment measures, but we expect that max 20% of the measures will be dropouts. The number of participants needed to be recruited in each group will therefore be $N = \frac{n}{1-dropout} = \frac{16}{0.8} = 20$. We want to compare four groups as defined in section IV.B. Study Population. The total number of participants will therefore be 80.

B. Statistical Methodology

The data will initially be analyzed by a series ANOVA test to compare each measurement between the four groups.

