To avoid 'mass significance' a combined analysis of all measurements will be performed by logistic regression models (LRM) in three steps. This will allow an estimate of the odds ratio and accuracy of each of the measurements and the measurements in combination. First, a series of univariate LRM will be performed for each measurement to investigate the odds ratio and accuracy of the individual. Second, a multiple factor LRM with all measurements as factors will be performed to estimate the odds ratio and accuracy for all measures in combination. Thirdly, factor reduction will be performed to assess the accuracy and odds ratio of a set of independent measures.

Simple bivariate correlation will be performed to further investigate the relation between measurements. Due to the complexity of the measurements a further analysis of the interdependency of the measures using factor analysis will be performed.

VII. DATA AND SAFETY MONITORING PLAN

The project will be reported to the Data protection Agency (DPA), and all sensitive data will be stored in either Red-CAP or on the protected server of Aalborg University Hospital, *"Elektronisk system adgang"* (ESA).

Data are stored in accordance with the stipulations in The Danish Personal Data Protection Act (Persondataloven) and other relevant Danish legislation. If any data processing would occur in foreign countries, the data will be anonymized and handled according to the Danish Data Protection Act.

The data can only be used for the interpretation of this project and will therefore not be of interest to third party.

The project is included in "Region Nordjyllands fællesfortegnelse".

VIII. STUDY LIMITATIONS

Both PTT and QST require corporation from the patients and include subjective measures of pain. As the measured thresholds are not purely objective, psychosocial factors might influence test results.

The study includes diabetic patients exclusively and might not be applicable on populations with different causes of neuropathy.

The expected number of participants are set at 80, thus maybe require additional larger studies to confirm findings.

IX. ETHICAL CONSIDERATIONS

A. Informed Consent

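### The plan describes no masking of examiners, image readers or analysts, although test accuracy is the main endpoint

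*Combined protocol and SAP*

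**What the plan says.** **Endpoint.** Section IV.A: "The main endpoint of the study will be sensitivity/specificity of all examinations", together with a comparison of newer and established methods.

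**How group is set.** Section IV.B defines DPN by biothesiometry or the 10 g monofilament. Section IV.D says of PainDETECT: "The patients will answer the questionnaire individually and will need to complete this before any other examinations can be conducted", the reason being "as this will help placing the patients in the correct group". The two clinical tests are usually done at the outpatient visit, or otherwise soon after inclusion and ahead of the experimental tests. The same paragraph, however, also allows the clinical examinations at any of the later sessions. Section V adds a record review, and gives its purpose: "This to ensure correct grouping of the patients and to make sure that they meet the inclusion criteria".

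**Who runs the tests.** For QST: "The test will be conducted by either PhD-students or research bio. med. lab. Technologist". Section IX.A lists the technologist, the principal investigator and the PhD-students as the people who should preferably inform participants. Section V places the principal investigator and one PhD-student at the recruiting centre. Section IV.C says only in general terms that "an experienced research Bio. Med. Lab. Technologist is signed for the project thereby, alongside the Ph.D.-students, ensuring trained personnel". Section IV.D names no operator for PTT and no reader for CCM or MRI. Nerve conduction is done by the neurophysiology department.

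**Masking.** The sections on procedures, data collection, statistical methods and limitations contain nothing on masking.

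**The concern.** In an accuracy study, a person who takes or reads the index test while knowing the reference classification can lean, without intending to, towards the expected answer. Cases then look more abnormal and controls more normal, so sensitivity and specificity both rise.

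QST leaves room for this. Filaments, pinpricks, brush strokes and the tuning fork are applied by hand, and several parameters are ratings that the participant speaks to the examiner. Image measurements can be affected in the same way when the reader knows the group.

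Because the bias need not be equal across tests, the comparison of newer with established methods could also be distorted. The main endpoint is where the effect would appear.

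**Working it through.** **Step 1. Is there a route from group to examiner?** Setting the sections side by side:
- Group information normally exists before the index tests, because PainDETECT comes first and the clinical tests usually precede the experimental ones.
- Where the clinical tests are moved to a later session, they may share that session with index tests.
- The QST staff categories overlap with those who inform participants, and one PhD-student works where patients are recruited and records are reviewed.
- Section IV.D allows healthy controls to be recruited from people whom staff know.

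The route is therefore open. The documents do not say that it is used.

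**Step 2. The plan's own figures.** Section VI.A gives means 14.4 and 5.7, SDs 4.7 and 7.5, and constant 15.7.
- Sum of variances: 4.7² + 7.5² = 78.34. Difference: 14.4 − 5.7 = 8.7.
- n = 15.7 × 78.34 / 8.7² = 16.25, which the plan gives as 16. Then 16/0.8 = 20 per group and 4 × 20 = 80.

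The stated size reproduces. Masking would not change it.

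**Step 3. What a given shift would do.** Common SD = √(78.34/2) = 6.26, so the separation is D = 8.7/6.26 = 1.39 SD. Assume normal measurements with equal variance, group as the reference, and an expectation shift of b SD. The documents give no value for b; 0.10 to 0.50 is an assumed range.
- AUC = Φ((D + b)/√2)
- Sensitivity = specificity at the midpoint cut-off = Φ((D + b)/2)

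| b (SD, assumed) | AUC, D = 1.39 | Sens. = spec., D = 1.39 | AUC, D = 0 |
|---|---|---|---|
| 0 | 0.837 | 0.756 | 0.500 |
| 0.10 | 0.854 | 0.772 | 0.528 |
| 0.50 | 0.909 | 0.828 | 0.638 |

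For a test with no real discrimination (D = 0), a two-sided 5% t-test with 20 per group would reject in 6.1% (b = 0.10) to 33.8% (b = 0.50) of studies, from the noncentral t distribution with noncentrality b/√(1/20 + 1/20) and 38 degrees of freedom.

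The value 1.39 comes from sensory nerve action potential amplitude, which is a nerve conduction measure. It is used because it is the only separation that the plan supplies; it is not an effect size for QST, PTT, CCM or MRI.

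**The case against.** The strongest reply is that the plan is silent on masking rather than opposed to it, and that much of what a reader might infer is not written there.

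- **That image reading is unmasked.** The documents do not say who reads CCM or MRI, when, or with what information. They support only that masking is not described. The appended flowchart is not reproduced in the text available and could hold operator details, although its surviving caption concerns session order and timing.
- **That the same staff run PTT.** No PTT operator is named, and the general remark about trained personnel does not fill that gap.
- **That QST examiners know the group.** This is a reasonable inference, not a stated fact. The clinical tests usually come from the outpatient visit, participants complete PainDETECT on their own, and its scoring block is marked for the doctor. The technologist's part in grouping is not stated.
- **That PTT is biased more than nerve conduction.** This is unproven. The PTT threshold is found by "slowly increasing the intensity of stimuli until the patient presses a button" and averaged over repeated presses, so examiner influence is less direct than in the hand-applied parts of QST. Thermal QST also ends on a button press.
- **That section VIII concedes examiner bias.** It says "As the measured thresholds are not purely objective, psychosocial factors might influence test results", which concerns the participant. Masking examiners would not remove that influence.

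All of this stands, and it limits what can be claimed. It does not close the gap: a study that follows the plan to the letter could run and read every index test with group in view.

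**Conclusion.** The point holds as a missing safeguard. With accuracy as the main endpoint, group normally set before the index tests, and no masking described for anyone, the estimates are open to upward expectation bias. The exposure is clearest for the hand-applied and verbally rated parts of QST. For PTT, CCM and MRI it follows from silence about who operates or reads.

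The direction rests on examiners or readers knowing the group and leaning towards the expected result. The size is unknown. The rise in AUC from 0.84 to between 0.85 and 0.91 only restates an assumed shift of 0.10 to 0.50 SD, applied to a separation borrowed from nerve conduction, and should not be read as an estimate for this study. No stated figure in the plan is in error on this account.

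**What to change.** Add three provisions to section IV.D:
1. CCM images and MRI data are coded, and the existing readers read them without access to group or to the biothesiometry, monofilament and PainDETECT results. Values are finalised before group is merged into the analysis file.
2. Where the rota allows, the person who did the grouping tests does not run QST or PTT on the same participant.
3. For each test, the operator or reader and whether that person was masked are recorded, and section VI.B gains a sensitivity analysis of accuracy by masking status.

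The cost is file coding and some constraint on scheduling; no new staff, visits or participants are needed. Operator masking will be incomplete, because the team is small and some controls may be known to staff. The sensitivity analysis will be imprecise with 20 per group, but it lets a reader judge the exposure. Coded reading is the most readily achieved of the three, and can still be applied to images already acquired but not yet read.

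### The sample-size formula counts the two-group factor twice: if 4.7 and 7.5 are the group SDs, 80% power needs 9 to 10 per group, and 16 per group gives about 97% power

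*Combined protocol and SAP*

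**What the plan says.** Section VI.A (Sample Size Considerations) sizes the study on one contrast, the ability to "separate a group of diabetic patients without neuropathy from a group of diabetes patients with 'moderate' neuropathy". The inputs come from "published measurement of the sensory nerve action potential amplitude in nerve fiber conduction assessments", cited to reference 45.

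The section first prints a general formula, n = 15.7σ²/d², with a single σ². In the numeric line that follows, the numerator is 15.7 times a sum of two squares ("15.7*(4.7^2+7.5^2") and the denominator is (14.4 − 5.7)². The conclusion is: "Setting the significance level to 0.05 and the power to 0.8 results in a sample size estimation of 16 persons in each group".

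The 16 is then divided by 0.8 for 20% dropout, giving 20 recruited per group and 80 over four groups. Section VIII (Study Limitations) repeats the 80. The text does not say what 4.7 and 7.5 are, whether the test is one- or two-sided, or why the two squares are added.

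**The concern.** The general and numeric forms do not match. The general form takes one variance and the numeric form puts in two added together. Since 15.7 is the constant for a two-group comparison with a common variance, adding the two group variances brings the number of groups in a second time and doubles the answer.

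This is the only sample-size justification in the plan, and both the 20 per group and the total of 80 follow from it. As printed, it tells the reader that 16 evaluable participants per group give 80% power for a difference of 8.7. If the two values are SDs, that is wrong. If they are something else, the 16 has no basis either, and the true power could be higher or lower than stated.

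**Working it through.** **Inputs, all from section VI.A:** significance level 0.05; power 0.8; d = 14.4 − 5.7 = 8.7, so d² = 75.69; the values 4.7 and 7.5, with squares 22.09 and 56.25; 16 per group; dropout 20%.

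**Assumptions:** 4.7 and 7.5 are the SDs of the two groups. The test is two-sided, as the constant implies: 2 × (1.960 + 0.842)² = 15.70, whereas a one-sided 0.05 test would give 12.4.

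**1. The plan's figure.** 15.7 × (22.09 + 56.25) / 75.69 = 15.7 × 78.34 / 75.69 = 16.25, printed as 16. The arithmetic reproduces (rounding up would give 17). The fault lies in what was substituted for σ².

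**2. The consistent forms.** For two equal groups with different SDs, n per group = (z₀.₉₇₅ + z₀.₈₀)² × (s₁² + s₂²) / d², where (1.960 + 0.842)² = 7.85. There are two equivalent ways to write it:

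- 7.85 with the sum: 7.85 × 78.34 / 75.69 = 8.12.
- 15.7 with the average variance, 78.34 / 2 = 39.17: 15.7 × 39.17 / 75.69 = 8.12.

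The printed 16.25 is therefore the unrounded total for both groups together.

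**3. Whole participants.** 8.12 rounds up to 9 per group, with power 0.839 by the normal approximation. A Welch t-test has power 0.780 at 9 and 0.828 at 10, so it needs 10. After 20% dropout: 9 / 0.8 = 11.25, so 12; or 10 / 0.8 = 12.5, so 13. The plan recruits 20.

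**4. Power for a difference of 8.7 at the planned sizes.** By the normal approximation, power = Φ(√(n × 75.69 / 78.34) − 1.96).

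- 16 per group: Φ(3.932 − 1.960) = Φ(1.972) = 0.976; Welch 0.965.
- 20 per group: Φ(4.396 − 1.960) = Φ(2.436) = 0.993; Welch 0.989.

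Simulation with unequal SDs agrees with the Welch figures (0.965 to 0.966 at 16 per group, 0.989 at 20).

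**5. Difference detectable with 80% power at 16 per group.** 2.802 × √(78.34 / 16) = 6.2 (normal), or 6.4 (Welch), against the stated 8.7.

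**6. Dependence on the SD reading.** At 16 per group, power falls below 0.8 once both true SDs exceed the printed values by a factor of 8.7 / 6.2 = 1.40 (normal) or 1.35 (Welch).

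**7. Other readings that might explain 16.** With the two values as group SDs, a one-sided test needs 7 per group, 90% power needs 11, and Bonferroni adjustment over 3 or 6 comparisons needs 11 or 13. Using the larger SD, 7.5, for both groups needs 12. None gives 16.

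**The case against.** The strongest reply is that little depends on the slip. If the values are SDs, the error is conservative: 16 per group more than meets the 0.8 target for this contrast, and no estimate, test or group definition in section VI.B uses the formula. That stands, and it is why recruitment need not change.

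A second reply is that the corrected figure could be misread as saying the study is oversized. That caution also stands. Section IV.A makes sensitivity and specificity of all examinations the main endpoint. Section VI.B plans ANOVAs across four groups and a logistic model with every measurement as a factor. None of these is sized, and section VIII already concedes that larger studies may be needed. The 8.12 says nothing about any of them.

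Third, nothing in section VI.A suggests that 4.7 and 7.5 are anything but SDs, so doubting the label may seem unwarranted. The formula does use them as SDs, and the corrected figures follow that reading. But the text does not label them and only the cited source can settle it, so the corrected n and power remain conditional. The inconsistency between the multiplier and the summed variance does not depend on the source.

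Finally, the choice between 9 and 10 per group is a matter of method. The plan uses a normal approximation, under which the answer is 9.

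**Conclusion.** The concern holds. The multiplier and the variance term in section VI.A do not belong together, and the printed n is twice what a consistent formula gives (16.25 against 8.12). No other section explains or corrects this.

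If 4.7 and 7.5 are group SDs and the test is two-sided at 0.05, the stated n is 1.6 to 1.8 times the requirement (16/10 to 16/9), and the power at 16 per group is 96.5% to 97.6%, not 80%. The error is then in the safe direction for the single contrast of no neuropathy versus moderate neuropathy. If the values are not SDs, neither the 16 nor the corrected 9 to 10 follows.

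The point concerns the correctness of a stated justification. It gives no ground for recruiting fewer participants.

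**What to change.** 1. Check in the cited source that 4.7 and 7.5 are SDs. Label them in section VI.A and state that the test is two-sided.

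2. If they are SDs, keep 20 per group and replace the calculation, for example with:

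   *For a two-sided test at 0.05 with SDs of 4.7 and 7.5, n = 7.85 × (4.7² + 7.5²) / (14.4 − 5.7)² = 8.1, so 9 per group (10 for a Welch t-test) gives 80% power for a difference of 8.7. We recruit 20 per group, more than the 12 to 13 needed after 20% dropout. With 16 evaluable per group, power is about 97% for the single contrast of no neuropathy versus moderate neuropathy. No power is claimed for other group pairs or other measures.*

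3. If they are not SDs, obtain the SDs and recalculate before printing any sample size or power.

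The cost is one look at the source and one rewritten paragraph. If the values are SDs, recruitment, procedures and participant burden stay as they are.
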